#### **10.1.4 Measurement Time Points**

Tumor size will be measured at study visits week 0, 4, and 8.

#### 10.1.5 Response Review

The primary outcome (tumor size) is measured in real time by a physician during the clinic visit; no radiologic images are obtained for later review in this study.

# 10.2 Secondary Outcomes

#### 10.2.1 Overall Adverse Events (AEs)

**Title**: Overall Adverse Events (AEs)

**Description**: Participants will be monitored for adverse events (AEs) throughout the study period. The outcome will be reported as the number of participants who experience any AE, serious or non-serious, a number without dispersion.

**Timeframe**: Up to 10 weeks

Safety Outcome?: Yes

#### 10.2.2 Serious Adverse Events (SAEs)

**Title**: Serious Adverse Events (SAEs)

**Description**: Participants will be monitored for serious adverse events (SAEs) throughout the study period. The outcome will be reported as the number of participants who experience any SAE, a number without dispersion.

Timeframe: Up to 10 weeks

Safety Outcome?: Yes

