#### **Study Completion:**

The study will reach study completion 24 months from the time the study opens to accrual, e.g., allowing 6 months from Primary Completion for data analysis. Individual subjects will complete the study about 14 to 18 weeks after starting topical remetinostat treatment (e.g., Screening; 8 weeks treatment; post-treatment visit and surgical excision at Week 10 to 14, 4 weeks follow-up).

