"Study medication is to be applied to dry skin. Apply the study medication to the SCC lesion(s) designated by your physician, 3 times daily for 8 weeks, using clean washed finger(s)/ hand as applicable. Cover the treated SCC lesions(s) with a sticky strip bandage, such as a Band-Aid. If you start to treat new lesions or stop treating any lesion, please inform your physician so a record can be kept of which lesions are being treated with study medication. There is no need to leave large amounts of residue on your skin. If someone else helps apply the study medication, they should follow the same instructions. Immediately following application, wipe the finger(s) and hands you have used to apply the study drug with a disposable tissue and wash your hands using soap and water. If the study medication gets on the skin of other people, they should wash with soap and water. Alternatively, you or a caregiver can wear disposable gloves to apply the study medication, which will be supplied to subject on request."

Diary: after an initial explanation by the study team at the first visit, patients will be requested to fill out a medication diary to document application of the study drug (see Appendix A.) Patients will be requested to fill this out daily and requested to bring their diary with them to each study visit for review by the study team.

Tumors to be treated will be clearly identified. Patients will be instructed to store research medication in a refrigerator (see Appendix B). Patients will be offered a small portable medication cooler to utilize to keep their study drug cold.

All tumors will be measured and photographed at baseline, 4 weeks and after applying remetinostat for 8 weeks (at the Week 10 visit).

Paper case report forms will be used to capture source data for this study. A physician note will also be entered into Stanford's electronic medical record system for each of the study visits.

Patients may be contacted periodically to check on compliance and to follow up on AEs. Additional clinic visit(s) may be scheduled to assess AEs.

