Given the absence of any remetinostat treatment related systemic AEs, together with the lack of effect on laboratory parameters or EKG, the minimal levels of remetinostat detected systemically reported in clinical studies to date, and the small BSA (< 0.5%) that will be treated with remetinostat gel, no lab assessments will be performed with the exception of a serum pregnancy test for women of child-bearing potential at baseline to assess eligibility for enrollment.

It is anticipated that the entire target tumor(s) will be surgically removed after the 8th week of treatment, in accordance with regular medical care; it is estimated that the surgical excision will occur between Weeks 10 to 14, depending on surgeon availability. A dose of remetinostat will be applied to the SCC by study personnel in clinic 30 mins before surgical excision. If surgical excision is delayed, i.e., does not occur at Week 10, remetinostat application may be continued for up to 4 additional weeks until surgical excision.

A follow-up visit will occur between Weeks 12 to 18 (approximately 2 to 4 weeks after Mohs/surgical excision), which may be in conjunction with surgery or a surgical follow-up visit,

or the visit may be conducted by phone. Patients may be contacted after completion of the study for additional follow up if deemed necessary by the Study Doctor.

SCC tissue biopsies will be collected from those who consent at baseline and Week 10 to evaluate the tumors treated with topical remetinostat gel 1%. The SCC biopsy will be collected in RNA later.

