#### 10. MEASUREMENTS

# For clinicaltrials.gov and Stanford Clinical Trials Directory compliance

# 10.1 Primary Outcome

**Title**: Overall Response Rate (ORR)

**Description**: The primary objective of this study is to determine if topical remetinostat will reduce squamous cell carcinoma (SCC) tumor size (measured in mm²). Tumors will be measured with calipers throughout the study. The associated outcome is reported as the number of tumors who achieve a partial response (PR) or complete response (CR), and overall response (OR). CR and PR are defined below, and OR is the sum of PR and CR.

- CR = undetectable tumor lesion(s).
- PR = ≥ 30% decrease in total tumor area.

Timeframe: Up to 10 weeks

Safety Outcome?: No

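### The Section 10.2 safety outcomes stop at 10 weeks although safety follow-up runs to Weeks 12–18; one common counting window should be stated (minor)

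*Combined protocol and SAP*

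**What the plan says.** Sections 10.2.1 to 10.2.4 cover AEs, SAEs, AE-related discontinuation or interruption, and treatment compliance. Each carries the same limit: "Timeframe: Up to 10 weeks". In 10.2.1 it stands beside "Participants will be monitored for adverse events (AEs) throughout the study period". Sections 10.2.2 and 10.2.3 say the equivalent; 10.2.4 does not.

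Other sections describe a longer period:

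- Section 3.4: "Individual subjects will complete the study about 14 to 18 weeks after starting topical remetinostat treatment".
- The Schema, Section 4 and the Section 9 calendar place a follow-up at Weeks 12–18, and the Schema gives safety monitoring as its purpose. Section 4 puts it roughly 2 to 4 weeks after excision, by visit or by phone, and allows a visit "which may be in conjunction with surgery or a surgical follow-up visit".
- The Section 9 footnote lets the Week 10 visit fall anywhere in Weeks 10–14.
- Section 7.2 has SAEs tracked to resolution or for 30 days from the last dose.
- On dosing, Section 4 asks subjects to stop at 8 weeks but also says "A dose of remetinostat will be applied to the SCC by study personnel in clinic 30 mins before surgical excision", with excision expected at Weeks 10–14. Section 4 and the Section 9 footnote allow up to 4 further weeks of application if surgery is delayed.

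Section 12.3 puts all AEs in tables. Sections 12.4.1 and 12.5.1 say whose data are included, and 12.5.2 lists the safety measures. None sets a time limit.

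Section 10 is headed "For clinicaltrials.gov and Stanford Clinical Trials Directory compliance", and Section 2.4 says there is no secondary outcome for ClinicalTrials.gov.

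**The concern.** Safety and tolerability make up the only secondary objective, and Section 10.2 is where it is turned into a stated metric, the number of participants affected. That metric carries a time limit that ends before a contact planned for safety monitoring.

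An analyst looking for a counting window finds only one given in weeks, in 10.2. Section 7.2 refers to a protocol-specified AE reporting period, but I did not find that period defined elsewhere in the document. If the 10.2 limit is applied, a subject whose first AE is noted at the follow-up visit appears in the Section 12.3 table and not in the 10.2.1 count. Both results would follow the protocol. With a dose given just before excision at Weeks 10–14, a literal Week 10 limit can also end at or before the last dose.

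**Working it through.** The plan gives no numerical result for this point, so the check is calendar arithmetic on its own weeks.

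**1. The plan's follow-up window.** Excision at Weeks 10–14 plus 2 to 4 weeks (Section 4): 10 + 2 = 12 and 14 + 4 = 18. This reproduces Weeks 12–18. Section 3.4 assumes 4 weeks of follow-up: 10 + 4 = 14 and 14 + 4 = 18, which reproduces 14 to 18 weeks.

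**2. Follow-up visit against the 10-week limit (10.2.1).**

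| Reading of the limit | Arithmetic | Weeks outside |
|---|---|---|
| Literal Week 10 | 12 − 10 to 18 − 10 | 2 to 8 |
| The Week 10 visit, held at Weeks 10–14 | 0 if follow-up is held with surgery, otherwise 2 to 4 after excision | 0 to 4 |

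Follow-up held with surgery fits Weeks 12–18 only when excision is at Weeks 12–14.

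**3. Thirty days after the last dose (7.2, relevant to 10.2.2).** 30 / 7 = 4.3 weeks.

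| Last dose | 30 days end at | Past Week 10 |
|---|---|---|
| Week 8 | 8 + 4.3 = 12.3 | 2.3 |
| Week 10 | 10 + 4.3 = 14.3 | 4.3 |
| Week 12 | 12 + 4.3 = 16.3 | 6.3 |
| Week 14 | 14 + 4.3 = 18.3 | 8.3 |

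For subjects who complete treatment, the 30 days therefore end at Week 12.3 to 18.3. The rows reflect the differing passages on dosing, and no choice among them is made here.

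Early stoppers differ. A subject sent to surgery because of growth at Week 4 (Section 6.1) has 30 days ending at 4 + 4.3 = Week 8.3. If no later follow-up visit is held, 0 weeks are lost.

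**4. Discontinuation, interruption and compliance (10.2.3, 10.2.4).** On the literal reading, a last application by Week 10 loses nothing. One at Week 12 leaves 12 − 10 = 2 weeks outside, and one at Week 14 leaves 14 − 10 = 4.

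**5. The same label on the primary outcome.** Section 10.1 has the identical limit. Section 10.1.4 names the last measurement as week 8, but Section 4 places the measurement after 8 weeks of treatment at the Week 10 visit. If that visit is held at Weeks 11–14, a literal limit would exclude the primary measurement as well.

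**The case against.** The strongest reply is that nothing need be lost. Section 10 is headed as registry text, and Section 2.4 disclaims any secondary outcome for ClinicalTrials.gov. The operative safety analysis is in Section 12, which sets no cut-off and would report every event collected. Monitoring for the whole study and reporting an outcome at a stated time are not strictly contradictory. All of this stands, and it makes the harm conditional on someone applying the 10.2 limit.

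A second reply is that 10 weeks probably means the Week 10 visit, as the primary outcome's identical label suggests (step 5). This also carries weight, and on that reading the loss can be zero. It does not settle the matter, because a separate follow-up 2 to 4 weeks after excision still falls outside, and the text does not say which reading is meant.

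Third, 7.2 speaks of tracking SAEs. It does not clearly say that new SAEs are sought for 30 days, so the figures in step 3 date a tracking limit and do not establish an onset window. That stands too.

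A reader might infer that late safety events go uncollected or unreported. The documents do not support this: the follow-up is planned and the Section 12 tables are open-ended. A reader might also infer a probability or number of missed participants, but the documents give no late-event rate from which to work one out.

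**Conclusion.** The inconsistency is real and minor. The 10.2 limit conflicts with whole-study monitoring, with the Week 12–18 follow-up and with completion at about 14 to 18 weeks. The follow-up visit lies 2 to 8 weeks outside a literal limit, or 0 to 4 weeks outside if the limit means the Week 10–14 visit. The possible consequence is that the 10.2 counts come out lower than the Section 12 tables.

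These are spans of calendar time taken from the plan's own weeks; they are not event counts, and no event count can be derived. The conclusion assumes only that the 10.2 limit might be applied as written. The literal reading should not be pressed for safety alone, since it would equally exclude primary tumour measurements made at Weeks 11–14. Power and sample size are not involved.

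**What to change.** In 10.2.1 to 10.2.4, replace the 10-week limit with one common window: from first dose through the end of the subject's participation, meaning the Week 12–18 follow-up visit, or the early-termination visit if there is no follow-up visit. Ending 10.2.3 and 10.2.4 at the last application would be weaker, because under Section 6.1 a permanent discontinuation can be decided after a period of suspension.

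Count any SAE recorded under 7.2 up to 30 days after the last dose in both 10.2.1 and 10.2.2. For example, with an excision dose at Week 10 and follow-up at Week 12, the 30 days run to Week 14.3. An SAE recorded at Week 13 would then count in both outcomes, and SAEs stay a subset of AEs.

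State in 12.5.2 that the AE tables and the 10.2 counts use this window.

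The cost is wording only. No visits are added, because the follow-up and the SAE tracking already exist, and no registry change is assumed given Section 2.4. The downside is that reported counts may be slightly higher. Separately, the sponsor must reconcile the passages on dosing duration in Section 4 and the Section 9 footnote, since the date of the last dose depends on them.

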#### 10.2.3 Adverse Event-related Treatment Discontinuation or Interruption

**Title**: Adverse Event-related Treatment Discontinuation or Interruption.

**Description**: Incidence of AEs leading to remetinostat discontinuation or interruption. Participants will be monitored for adverse events (SAEs) throughout the study period, and the relationship of remetinostat discontinuation or interruption to adverse events will be evaluated for all remetinostat discontinuation or interruption. The outcome will be reported as the number of participants who discontinued remetinostat or experienced treatment interruption due to an adverse event, a number without dispersion.

Timeframe: Up to 10 weeks

Safety Outcome?: Yes

#### 10.2.4

Title: Treatment Schedule Compliance

**Description**: Participant adherence to the treatment schedule will be assessed as the number of patients who discontinue the treatment, or experience treatment interruption, for any reason. The outcome will be reported as a number without dispersion.

Timeframe: Up to 10 weeks

Safety Outcome?: Yes

#### 11. REGULATORY CONSIDERATIONS

#### 11.1 Institutional Review of Protocol

The protocol, the proposed informed consent and all forms of participant information related to the study (eg, advertisements used to recruit participants) will be reviewed and approved by the Stanford IRB and Stanford Cancer Institute Scientific Review Committee (SRC). Any changes made to the protocol will be submitted as a modification and will be approved by the IRB prior to implementation. The Protocol Director will disseminate the protocol amendment information to all participating investigators.

## 11.2 Data and Safety Monitoring Plan

The Stanford Cancer Institute Data and Safety Monitoring Committee (DSMC) will be the monitoring entity for this study. The DSMC will audit study-related activities to determine whether the study has been conducted in accordance with the protocol, local standard operating procedures, FDA regulations, and Good Clinical Practice (GCP). This may include review of the following types of documents participating in the study: regulatory binders, case report forms, eligibility checklists, and source documents. In addition, the DSMC will regularly review serious adverse events and protocol deviations associated with the research to ensure the protection of

human subjects. Results of the DSMC audit will be communicated to the IRB and the appropriate regulatory authorities at the time of continuing review, or in an expedited fashion, as needed.

#### 11.3 Data Management Plan

The Protocol Director, or a designee, will prepare and maintain adequate and accurate participant case histories with observations and data pertinent to the study. Study-specific case report forms (CRFs) will be developed to document treatment outcomes for data analysis. These CRFs will initially be developed on paper forms by the study coordinator but may transition to electronic forms (ie, in OnCore or RedCap). Subject charts will be kept in a locked office, only accessible to the research team.

#### 12. STATISTICAL CONSIDERATIONS

[name], MS, is the statistician for this clinical trial.

# 12.1 Statistical Design

The Primary Objective and Primary Outcome of this study is to determine if topical remetinostat will reduce SCC tumor size, as defined by at least 30% decrease in SCC tumor area (in mm²) at end of study as compared with baseline. Complete response (CR) will be defined as no clinically detectable tumor at EOS. ORR is defined as the proportion of tumors with either a complete response or a partial response (PR) among all eligible and treated lesions. Exact binomial 90% confidence intervals (CIs) will be computed for the ORR. With a planned analysis on 30 per-protocol SCCs, this study should provide 91% power to reject an ORR of 15% if the true ORR is 40% or better, at one-sided-alpha level of 0.05 with at least 9 responders.

#### 12.1.1 Randomization

Not applicable, as this is a single-arm trial.

# 12.2 Interim analyses

None planned

#### 12.3 Descriptive Statistics and Exploratory Data Analysis

The baseline characteristics of study subjects (age; gender; skin type; number of tumors; average size of tumors; tumor location; tumor histology; and prior treatments) will be summarized in tables. Wilcoxon signed rank tests for continuous variables and chi-square tests for dichotomous variables will be used. CONSORT guidelines will be followed to describe the number of subjects screened; enrolled; and completed the treatment. All AEs will be described in tabular format.

#### 12.4 Primary Analysis

The primary endpoint is the overall response rate of SCC lesions as defined by at least 30% decrease in tumor area at EOS as compared to baseline. Note: RECIST v1.1 criteria have limited utility for SCCs under 10 mm, and will not be used for that reason.

#### 12.4.1 Analysis Population

We will first analyze the data by intention to treat analysis and then per-protocol analysis by only including tumors ≥ 80% compliant with drug treatment. Tumors with 79% or less compliant with

drug treatment will be reported as a deviation; tumors at least 80% compliant with drug treatment will not be recorded as a deviation. Patients will be instructed to use a band-aid or other form of occlusion. If the patient has difficulty with band-aid usage, the patient may stop and this will be documented.

For subjects who drop out, we will use data from their last study visit if they contribute a biopsy. The analysis population will include participants who have consented to undergo remetinostat treatment and who have at least 1 SCC tumor.

Safety analyses will include all subjects who received at least one dose of study treatment. Graded AEs (number and percent) will be summarized and reported according to the NCI CTCAE v5.0.

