#### 12.4.2 Analysis Plan

We will analyze the overall response rate of SCC based on the change in tumor area. Objective response rate (ORR) will be defined as the proportion of tumors with either a complete response or a partial response (PR) among all eligible and treated tumors. Toxicities will be graded according to the National Cancer Institute CTCAE v5.0. Exact binomial 90% confidence intervals (CIs) will be computed for the ORR. With a planned analysis on 30 per-protocol SCCs, this study would provide 91% power to reject an ORR of 15% if the true ORR is 40% or better, at one-sided alpha level of 0.05 with at least 9 responders.

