#### 12.6 Sample Size

#### 12.6.1 Overall Accrual estimates

Subjects will be enrolled from Stanford Dermatology (Adult) clinic which sees approximately 4,000 dermatology patients per month (or 48,000 visits per year). Approximately 20% of these patients have current or past skin cancer. Enrollment of SCC subjects for Stanford clinical trials has been rapid. 30 per-protocol SCC lesions are anticipated to be evaluated within the first 12 months. We will only advertise and enroll from Stanford Dermatology clinic. It is anticipated that at least 10 subjects will consent to baseline and post-treatment biopsies.

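### Section 12.4.1 uses a dropout's last-visit data only on condition of an unspecified biopsy, although response is a caliper measurement, and does not state how an unmeasured treated lesion is scored

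*Combined protocol and SAP*

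**What the plan says.** Section 12.4.1 orders the analyses: "We will first analyze the data by intention to treat analysis and then per-protocol analysis", the second limited to tumors at least 80% compliant. For dropouts it adds: "For subjects who drop out, we will use data from their last study visit if they contribute a biopsy". The next sentence sets a population with no tissue condition: "The analysis population will include participants who have consented to undergo remetinostat treatment and who have at least 1 SCC tumor".

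The response rate is defined twice. The denominator is "among all eligible and treated lesions" in Section 12.1 and "among all eligible and treated tumors" in Section 12.4.2. Section 10.1.1, in contrast, limits the analysis to tumors with at least 80% compliance and does not name an analysis set.

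On how response is measured, Section 10.1 says: "Tumors will be measured with calipers throughout the study". Sections 10.1.2 to 10.1.5 describe caliper measurements taken by a physician at the visit. The calendar in Section 9 marks tumor measurements and photographs in its early-termination column; as the table reads in the public text, no biopsy is marked there.

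On tissue, Section 4 says: "SCC tissue biopsies will be collected from those who consent at baseline and Week 10". Section 12.6.1 says: "It is anticipated that at least 10 subjects will consent to baseline and post-treatment biopsies".

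**The concern.** The condition has no link to the endpoint. Partial response is a fall of at least 30% in measured area, and complete response is the absence of a clinically detectable tumor. Neither uses tissue. Two dropouts with the same caliper readings could therefore be handled differently because one agreed to a research biopsy and the other did not.

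Dropout is not remote in this protocol. Section 6 takes off study any subject who must discontinue treatment, for whatever reason. The early-termination visit collects the very measurement that the endpoint needs, and Section 12.4.1 may then set it aside.

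At stake is the intention-to-treat response rate and its exact 90% confidence interval. This is the analysis that Section 12.4.1 names first, and as written its result depends on a reading that could be settled after the data are seen.

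**Working it through.** **1. The plan's own figure.** Inputs from Section 12.6.2: 30 tumors, at least 9 responders, reference rate 15%, alternative 40%, one-sided alpha 0.05. Exact binomial tails:

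- P(X ≥ 9 | n = 30, p = 0.15) = 0.028
- P(X ≥ 9 | n = 30, p = 0.40) = 0.906

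The stated 91% power reproduces. It belongs to the per-protocol tumors.

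**2. Which biopsy?** The documents allow several meanings:

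- Diagnostic biopsy (Sections 2.4 and 4): recruitment requires at least one biopsy-proven lesion, so the condition removes few or none.
- Research biopsies at baseline and Week 10 (Schema, Section 4): taken only with consent. A dropout before Week 10 may have only the first.
- A biopsy at excision, labelled Week 8 in Section 4: optional.

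Another sentence in Section 4 reads as if every subject consents to donate tissue. Section 12.4.1 chooses none of these.

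**3. What happens to a dropout's lesion whose data are not used?**

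- *Kept as a non-response*, as the denominators in Sections 12.1 and 12.4.2 imply. The condition then touches only the numerator. A measured response can be lost and none can be gained, so the rate falls or stays the same.
- *Left out.* This contradicts those denominators, the population sentence in Section 12.4.1 and the intention-to-treat label. The rate rises if dropouts respond less often than completers, falls if they respond more often, and is unbiased if they respond alike.

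**4. Illustrations.** The documents give no dropout rate, so the counts below are assumptions. Lesions are treated as independent, although a subject may contribute several. The lower limit of the exact two-sided 90% interval for x responders of n is the 5% quantile of Beta(x, n − x + 1).

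*One dataset, three readings.* Assume 34 treated lesions and 10 measured responses, one of them in a dropout without the required biopsy.

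| Handling of that lesion | Rate | Lower 90% limit |
|---|---|---|
| Measurement used | 10/34 = 29.4% | 16.9% |
| Left out | 9/33 = 27.3% | 15.03% |
| Measurement discarded, lesion kept | 9/34 = 26.5% | 14.6% |

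*Dropouts without usable data added as non-responders.* Starting from 9/30 = 30.0% (lower limit 16.6%), three more give 9/33 (15.03%) and four give 9/34 (14.6%), which no longer excludes 15%. With 10 responders, eight can be added and 15% is still excluded (10/38 = 26.3%, lower limit 15.03%). With 12, adding ten moves the estimate from 12/30 = 40.0% (25.0%) to 12/40 = 30.0% (18.3%), and the conclusion against 15% stands.

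*Upper bound on upward bias if such dropouts are left out.* Take 40 treated lesions, a true rate of 15% (0.15 × 40 = 6 expected responders), d dropouts, none with a biopsy, responding at r times the completer rate. The expected rate is then the completer rate, 6 / ((40 − d) + d·r):

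- r = 0: 6/36 = 16.7% for d = 4; 6/30 = 20.0% for d = 10
- r = 0.5: 6/38 = 15.8% for d = 4; 6/35 = 17.1% for d = 10
- r = 1: 6/40 = 15.0%, no bias

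If every dropout has a biopsy, nobody is left out and the rate is 15.0% throughout.

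**The case against.** The strongest reply is that the plan already contains the scoring rule. The response rate counts tumors with a complete or partial response over all eligible and treated tumors, so a treated lesion with no documented response is in the denominator and not in the numerator. The biopsy sentence does not expressly remove anyone. This largely stands. A reader might infer that the plan drops dropouts from the denominator and so inflates the response rate. The documents do not support that as the natural reading, because two definitions and the sentence that follows the biopsy condition point the other way. What remains is that non-response is implied and not stated, that Section 10.1.1 points to a narrower set, and that measured responses may be discarded.

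A reader might also infer that the lost lesions are mainly failures, since Section 6.1 directs subjects with lesions that have grown by 30% to surgery and Section 4.2 takes lesions above 20 mm off treatment. This is weak. Growth under Section 6.1 is found by a Week 4 measurement, so response data exist, and tissue may be collected at excision. Nothing shows that these subjects are the ones without a biopsy.

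Nor can the expectation of at least 10 consenting subjects, out of at most 40, be read as the share of dropouts who have a biopsy. It is a floor, it concerns consent to both biopsies, and it counts subjects, not lesions.

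Finally, the 9-responder examples sit on the decision boundary, and early-termination measurements should keep the number of unmeasured lesions small. Both points are fair and limit the size of the problem. They do not explain why tissue should decide whether a measurement is used.

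**Conclusion.** The concern holds and should be fixed before analysis. Section 12.4.1 makes the use of valid caliper data depend on a biopsy that it does not identify and that the endpoint does not need. Read with the plan's denominators, the condition lowers the intention-to-treat response rate whenever a dropout's measured response is discarded. Upward bias requires a reading that Sections 12.1 and 12.4.2 contradict, together with dropouts who respond less often than completers.

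The size cannot be fixed, because no dropout rate is given. Near 9 responders, one discarded response or four added non-responders can move the lower 90% limit across 15%. Further from that boundary the conclusion does not change.

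A reader might infer that the trial's error rate or power is compromised. It is not: alpha 0.028 and power 0.906 belong to the 30 per-protocol tumors, and the Synopsis plans enrollment to obtain 30 evaluable tumors. That analysis is largely unaffected, though not wholly, because a dropout who still meets 80% compliance could fall within it.

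**What to change.** In Section 12.4.1, delete the biopsy condition and state three things:

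1. For a subject who drops out, the last available post-baseline caliper measurement, including one from the early-termination visit, is used whether or not tissue was given.
2. Every eligible treated lesion is in the intention-to-treat denominator, and a lesion with no post-baseline measurement counts as a non-responder.
3. The 80% compliance restriction in Section 10.1.1 applies to the per-protocol analysis only.

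The exact 90% interval is then computed on the actual intention-to-treat number of lesions. As an optional sensitivity analysis, count every lesion without an end-of-study measurement as a non-responder.

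The cost is a few sentences, with no new visits, biopsies or data. The intention-to-treat rate may move slightly in either direction. A last-visit measurement can also credit shrinkage that was not sustained, which the sensitivity analysis would show.
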